1. *Adult Asthma History* includes 5 items adapted from the Behavioral Risk Factor Surveillance System Survey.⁷⁴ Four items address participants' recent contact with healthcare professionals for asthma since COVID-19. The final item addresses changes in routine work/activities due to asthma since COVID-19.
2. *Asthma Control Test (ACT)*. The ACT includes 5 items addressing: asthma symptoms, use of rescue medications, and effect of asthma on daily functioning. Responses are summed for total ACT score.^{75,76}
3. *Airborne Exposures*. The 7 items from the PROMISSM Pool V1.0 Dyspnea Airborne Exposure address airborne allergens, pollutants, smoke, pets, and use of pesticides using Yes:No response options.⁷⁷
4. *Adult Asthma Adherence Questionnaire*,TM includes 5 items on following their prescribed asthma medication plan and barriers to following that plan.⁷⁸
5. *Health and Demographics* includes items such as self-rated physical health, comorbidities, height/weight, age, education, ZIP code, smoking status, and COVID-19 prevention practices, and COVID-19 exposure/infection status.
6. *Home Environmental Exposure* data will be gathered including home type, # of occupants, vacuum with HEPA filter, cleaning practices, cleaning products, air filter, heating, ventilation, smoke exposures, hand washing practices, pests, hobbies, odors, indoor plants, printers, flooring, and stove type.^{79,80}

We will also measure the following psychometrically valid measures as potential confounders:

7. *Emotional Distress-Anxiety and Depression PROMIS Short Forms 4a* assess anxiety and depression levels within the last 7 days (4 items). Higher scores indicate higher severity of anxiety or depression.^{81,82}
8. *Emotional Support*, PROMIS_SF_V2 Short Form 4A measures perceived feelings of support, being cared for and valued (4 items).⁸³ Higher score indicating a higher perceived emotional support.
9. *Perceived stress scale* includes 4 items measuring the degree to which situations in one's life are appraised as stressful.⁸⁴⁻⁸⁶ Higher scores indicate an increased level of perceived stress.

EMA survey items (See Appendix).

- *Asthma symptoms* (trouble breathing, wheezing, coughing, other symptoms [Yes:No]) assessed each time participants are asked to complete an EMA survey.
- *Random EMA surveys (twice/day)* assess use of disinfectants/cleaners in last 2 hours (Yes:No) if Yes, the type, brand, and asthma symptoms are queried.

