We will also assess the duration the indoor air quality monitor is used by each participant. The quantitative participant feasibility assessment of acceptability, appropriateness, and feasibility will be analyzed descriptively. In addition, we will examine differences in use/acceptance by participant characteristics (e.g., age, asthma symptoms, overall health, education, etc). Qualitative interview data will be transcribed, uploaded into Dedoose qualitative analysis software for content analysis.

Aim 2a: We will collect baseline data on the current frequency and degree of disinfectants/cleaners and exposure to environmental triggers (e.g., secondhand smoke). We will capture real-time self-reported data on disinfectant use throughout the study period. We will determine the prevalence of disinfectant/cleaner use and frequency (% EMA prompts at which disinfectant/cleaner use is reported). We will obtain data from the Awair dashboard to determine the number of times VOCs and PM_{2.5} levels exceed optimal levels, average daily levels, average levels per time period, and fluctuations in VOC and PM_{2.5}. We will identify possible environmental triggers that contribute to high levels of VOCs and PM_{2.5} leading to event-contingent prompts.

[figure not shown]
Aim 2b: We will determine baseline level of asthma control as measured by the ACT. We will use EMA to determine the level of asthma control over the study period as indicated by (a) asthma symptoms reported at each prompt and over the 14 days; (b) number of time-periods during which an EMA prompt is sent and participants report asthma symptoms; and (c) lung function as measured by FEV₁% predicted at each prompt. Asthma control will also be evaluated using EMA by exploring differences in variability in lung function.

Aim 3: Data collected using the EMA approach are multilevel with time windows (level 1) nested with individuals (level 2). The exposure variables will include: (1) Baseline self-reported use and frequency of disinfectant/cleaner use and PM_{2.5} exposures; (2) Number of times VOC and PM_{2.5} levels exceed the threshold for the optimal readings per week; and (3) Average scores of VOC and PM_{2.5} levels in the time windows considered in the analysis. The outcome variables we will consider include occurrence of any asthma symptoms, inhaler use, and FEV₁% predicted (within 30 minutes of each EMA prompt).

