We will use multi-level binary logistic regression to examine the associations of the exposure variables with the binary outcome variables. We will use multilevel linear regression to examine the associations of the exposure variables with FEV₁% predicted. We will control for level 1 variables (time of day, day of week) and level 2 variables (baseline asthma symptoms, demographic characteristics, and psychosocial characteristics). Using available time stamps from the indoor air quality monitor, EMA, and the spirometer, we will also explore average lag time between an event-contingent prompt and self-reported asthma symptoms using multilevel survival analyses.

Summary

The proposed study has several strengths. First, our study is innovatively addressing the increased use of disinfectants during COVID-19 in adults with asthma. The study builds on an ongoing study and will be conducted with individuals who have agreed to be recruited for future studies and facilitate recruitment. Furthermore, participants will be drawn from a wide geographic area in the US which increases broad representation of participants. Moreover, we will uniquely gather real time environmental exposure data and indicators of asthma control in unregulated indoor residential space without actual in-person contact. Finally, findings from this study have the potential to impact recommendations for indoor use of disinfectants/cleaners for those with asthma and will guide further research.

References

1. Center for Disease Control and Prevention. Asthma. FastStats web site. <https://www.cdc.gov/nchs/faststats/asthma.htm>. Published 2018. Accessed Date.
2. Center for Disease Control and Prevention. AsthmaStats. https://www.cdc.gov/asthma/asthma_stats/default.htm. Published 2020. Accessed Date.
5. Center for Disease Control and Prevention. Coronavirus (COVID-19). <https://www.cdc.gov/coronavirus/2019-nCoV/index.html>. Published 2020. Accessed Date.

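### Aim 3 does not separate within-person from between-home variation in window-average VOC and PM2.5, so each coefficient, run as written, is a mix of the two

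*Combined protocol and SAP*

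**What the plan says.** The Aim 3 text under Data Analysis treats time windows as level 1 and individuals as level 2. It lists three kinds of exposure:

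- "Baseline self-reported use and frequency of disinfectant/cleaner use and PM_{2.5} exposures": one value per person.
- "Number of times VOC and PM_{2.5} levels exceed the threshold for the optimal readings per week": at most about two values per person in 14 days.
- "Average scores of VOC and PM_{2.5} levels in the time windows considered in the analysis": a value that changes from window to window.

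The models are "We will use multi-level binary logistic regression to examine the associations of the exposure variables with the binary outcome variables" and "We will use multilevel linear regression to examine the associations of the exposure variables with FEV₁% predicted". On adjustment the plan states "We will control for level 1 variables (time of day, day of week) and level 2 variables (baseline asthma symptoms, demographic characteristics", and the list closes with psychosocial characteristics. Home features are recorded under Baseline Measures, where "data will be gathered including home type, # of occupants, vacuum with HEPA filter, cleaning practices, cleaning products, air filter, heating, ventilation", but the Aim 3 adjustment set names none of them.

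The documents do not mention person-mean centring, a person-mean exposure term, fixed person effects, or separate within-person and between-person results. The Innovation section gives real-time study of how triggers affect symptoms as the reason for using EMA. The Specific Aims describe Aim 3 as exploring associations.

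**The concern.** Window-average VOC and PM2.5 vary in two ways: over time within one home, and between homes in their usual level. The within-person slope asks whether a person does worse when the air at home is worse than usual for that home. The between-home slope asks whether people in homes with worse air do worse in general. Fixed features of the home or person, such as pets, pests, ventilation or stove type, can confound the second but not the first.

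A random intercept does not keep the two apart. If the exposure enters uncentred, one coefficient averages both slopes. A home-to-home difference could then be reported as a real-time association. The Specific Aims offer the results as preliminary data for a powered study, and the Summary says they may affect recommendations on disinfectant use.

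The Particulates paragraph hints that the slopes may differ. It cites a comparison between people in which poorly controlled older adults had higher maximum PM2.5 (p=.03). It also cites 12 weeks of repeated monitoring in 26 people with no consistent relation to daily outcomes. Populations and measures differ, so this is only suggestive.

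**Working it through.** The plan states no ICC, effect size or power for Aim 3, so there is no figure of its own to reproduce. The check asks how much of a single coefficient comes from between-home differences.

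**Inputs from the documents.** Fifty participants (Sample). Four 4-hour periods a day (Data Analysis) for 14 days (Procedures) give at most 4 × 14 = 56 windows per person. Scheduled surveys are one each morning plus two random ones a day, so 3 × 14 = 42 before any triggered by the monitor.

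**Assumptions.** One home per participant; a random-intercept model; analysed windows per person n = 15, 30 or 56; exposure ICC (ICCx) 0.3, 0.5 or 0.8; outcome ICC (ICCy) 0.3 (plausible for symptoms) or 0.8 (plausible for FEV1% predicted).

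**Formula (linear random-intercept weights).** With total residual variance 1, t² = ICCy and s² = 1 − ICCy. Per person:

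- Between information: B = [n·ICCx + (1 − ICCx)] / (s² + n·t²)
- Within information: W = (n − 1)(1 − ICCx) / s²
- Between-home share: w = B / (B + W)
- Single coefficient = w × between slope + (1 − w) × within slope

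**Worked cases.**

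- ICCy 0.3, ICCx 0.8, n = 15: B = 12.2/5.2 = 2.346; W = 14 × 0.2/0.7 = 4.000; w = 2.346/6.346 = 37%.
- Same ICCs, n = 56: B = 45/17.5 = 2.571; W = 55 × 0.2/0.7 = 15.714; w = 14%.
- ICCy 0.3, ICCx 0.5, n = 30: B = 15.5/9.7 = 1.598; W = 29 × 0.5/0.7 = 20.714; w = 7%.
- ICCy 0.8, ICCx 0.8, n = 15: B = 12.2/12.2 = 1.000; W = 14 × 0.2/0.2 = 14.000; w = 7%.

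Between-home share in the single coefficient:

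| Outcome ICC | Windows | ICCx 0.3 | ICCx 0.5 | ICCx 0.8 |
|---|---|---|---|---|
| 0.3 | 15 | 6.7% | 13.3% | 37.0% |
| 0.3 | 30 | 3.3% | 7.2% | 23.1% |
| 0.3 | 56 | 1.8% | 4.0% | 14.1% |
| 0.8 | 15 | 0.9% | 1.8% | 6.7% |
| 0.8 | 30 | 0.4% | 0.9% | 3.3% |
| 0.8 | 56 | 0.2% | 0.5% | 1.8% |

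**Check in the logistic model.** The weights above are for a linear model, so a random-intercept logistic model was simulated with 50 people and 30 replicates per scenario. Scenarios used 14 or 56 windows, exposure ICC 0.5 or 0.8, and latent outcome ICC 0.1 or 0.3. With a true within slope of 0 and between slope of 1.0, the single raw term averaged 0.07 to 0.65. At 56 windows, exposure ICC 0.8 and latent outcome ICC 0.3 it averaged 0.17, close to the 0.14 that the linear weights predict. The 0.65 came from 14 windows, exposure ICC 0.8 and latent outcome ICC 0.1, which lies below the outcome ICCs in the table.

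With person mean and deviation entered separately, the within slope was recovered: −0.02 to 0.04 when the truth was 0, and 0.47 to 0.52 when it was 0.5. Thirteen of 16 scenarios finished. The three that did not all had 14 windows and exposure ICC 0.8.

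**The case against.** The strongest reply is that the plan is silent rather than wrong. A reader might infer that Aim 3 commits to one raw term per exposure, but the text does not say raw, random-intercept or one exposure per model. If weekly counts or baseline exposure entered the same model, they would absorb part of the between-home contrast. This stands as a limit on the wording. It does not remove the point, because joint entry is not specified and neither variable is the person mean.

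The larger figures need several assumptions at once. The 37% case requires exposure ICC 0.8, outcome ICC 0.3 and 15 windows; fifteen answers is 15/42 = 36% of scheduled surveys, with none triggered by the monitor. At 42 windows and the same ICCs the share is 33.8/13.3 = 2.541 over 2.541 + 11.714, or 18%. This stands.

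A reader might also infer that no Aim 3 coefficient can be read as a real-time association, or that its sign could be reversed. The documents do not support either. The share is small over much of the range, above all for FEV1% predicted, and nothing suggests that the two slopes have opposite signs. Nor is background severity left uncontrolled, since baseline asthma symptoms are adjusted for.

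Finally, Aim 3 is exploratory and no decision rule rests on it. That limits the seriousness, but not the need to know which question a coefficient answers when it feeds a later study.

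**Conclusion.** The point holds for window-average VOC and PM2.5. The plan gives a real-time purpose but does not say how the within-person association will be isolated, and the model as written does not isolate it.

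The contamination is at most about 7% for FEV1% predicted if its ICC is near 0.8. It can matter for symptoms and inhaler use: about 14% to 37% if outcome ICC is 0.3 and homes differ stably in exposure (ICC 0.8), but only about 4% to 7% at exposure ICC 0.5 with 30 to 56 windows. All ICCs and the numbers of analysed windows are assumptions.

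The point does not apply to baseline exposure, which varies only between people, and applies only weakly to weekly counts. It concerns interpretation and the design of the next study. It is worth correcting because the remedy is cheap and needs no new data.

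**What to change.** For each window-average exposure, enter two terms: the person's mean over the windows included in that particular model, and the window's deviation from that mean. Name the deviation coefficient in advance as the real-time (within-person) association. Report the person-mean coefficient separately, as exploratory and open to confounding by home features.

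The mean should come from the analysed windows, not from all 14 days of monitor data. High readings trigger prompts, so analysed windows are not a random sample of the period. Deviations from a 14-day mean would not average zero within a person, and would carry some between-home variation back into the within term.

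The cost is plan wording, one extra term per exposure, and a somewhat wider interval. In the linear model the standard error of the within slope, relative to the single coefficient, grows by √[1/(1 − w)]: about 8% at w = 0.14 and 26% at w = 0.37. That lost precision came from the between-home comparison, which does not answer the real-time question.

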The Changing COVID-19 Landscape: A Feasibility Study to
Capture Momentary Residential Environmental Exposures and
Asthma Symptoms in Adults

NCT05224076

March 13, 2025

SPECIFIC AIMS

The global pandemic of coronavirus 2019 (COVID-19) has rapidly impacted the United States (US) population and is a substantial cause for concern among individuals with chronic respiratory diseases. Asthma is a complex, multi-faceted respiratory disease that affects over 19 million US adults (18 years or older).¹ Further, it is estimated that more than 60% of US adults with asthma have uncontrolled symptoms.² This represents a substantial health and economic impact; uncontrolled asthma in the US results in the loss of approximately 15 million quality-adjusted life years among adults and a total economic burden (both direct and indirect costs) of greater than \$960 billion over a 20-year span.³ In addition, adults appear to be nearly five times more likely to die from asthma than children and the asthma-related death rate is highest among those 65 years and older.² Viral infections are a prominent risk factor for asthma exacerbation⁴ and, thus, SARS-CoV-2, the virus responsible for COVID-19, is cause for alarm among those diagnosed with asthma. Sheltering-in-place orders and recommendations, physical distancing, wearing face coverings, hand hygiene, and increased cleaning and disinfecting are primary COVID-19 preventative measures advocated by public health experts.⁵ What is not known are the effects of these preventive measures, specifically increased residential exposure to cleaning/disinfecting agents and other environmental exposures on adults with asthma.

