Gharpure et al.⁴⁸ reported that since the COVID-19 pandemic, 60% of respondents to an online US survey had increased cleaning/disinfecting since the pandemic. Over a third of survey respondents indicated they had engaged in at least one high-risk practice involving a disinfectant such as bleaching food, using a household disinfectant on their hands, or misting themselves with a cleaner/disinfectant.⁴⁸ What is not known is the extent that adults with asthma engage in these types of practices, how often they clean/disinfect, and what impact these practices have on their asthma.

Particulates. Particulate matter (PM) are small particles/liquid droplets that include acids, organic chemicals, metals, soils, dust, and allergens.⁴⁹ Common indoor sources of particulates include outdoor sources, vacuum cleaner bags, printers, cooking, secondhand smoke, wood combustion in fireplaces/stoves, dust, pet hair, mold, candles, and biological sources.^{25,50} PM_{2.5} concentrations were found to be highest indoors

in homes (vs. outdoors or in offices) on weekends when participants wearing personal air quality monitors were home for longer periods,⁵¹ thus supporting the increased potential exposure to particulates during the COVID-19 pandemic. PM_{2.5}, or particulates less than 2.5 micrometers, have been shown to affect cardiovascular health, anxiety, cognitive function, and respiratory health.⁵⁰ The effects of PM_{2.5} on asthma are unclear. When nighttime particulates were monitored for 12 weeks in individuals with asthma sensitized to house dust mites (N=26), no consistent relationship was found between PM exposure and daily clinical outcomes (peak expiratory flow, FeNO, symptoms).⁵² In contrast, increased indoor particulates were significantly related to reduced lung function, specifically with candle burning.²⁵ Increased frequency and severity of asthma exacerbations, asthma symptoms, hospitalizations, and asthma mortality were associated with increased ambient PM_{2.5}.⁵³⁻⁵⁶ Polivka et al.,⁵⁷ found that older adults with poorly controlled asthma had significantly greater maximum PM_{2.5} counts over a 24-hour period (p=.03).

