- *EMA survey triggered by VOCs/PM_{2.5} greater than optimal range as detected by the Awair* will query asthma symptoms, lists of probable sources of elevated VOCs or PM_{2.5}.
- *EMA survey 30-minutes after Awair air quality notification* queries mitigation strategies used (from lists) and asthma symptoms.
- *Home spirometer use* (Yes:No) queried in each EMA survey

Home spirometer. FEV₁% predicted– a standard metric of lung function for those with asthma.

Seven-Day check-in. Open-ended questions to identify any trouble-shooting areas, determine if adjustments need to be made, and assess ease of use of the app/devices. Interactions will be recorded and reviewed by the research team for patterns and to identify any adjustments that are needed.

Participant feasibility assessment. At the end of the 14-day data collection period, participants will be asked to respond to a short REDCap survey assessing acceptability, appropriateness, and feasibility of the indoor air quality monitor, EMA notifications, and the home spirometer with response ranging from 1=completely disagree to 5=completely agree. A random sample of 20 participants will be interviewed to further explore these factors using open-ended questions such as "Tell us what you liked/didn't like about the indoor air quality monitor", "Describe the strengths/concerns about the survey you received about your home indoor air quality".

Data Analysis

Each day of observation will be divided into four 4-hour periods between 6 a.m. and 10 p.m. Data from a given period will be considered as follows:

1. Period specific data from all event-contingent EMA prompts [prompts triggered by high indoor air VOC/PM_{2.5} readings] will be analyzed. If multiple event-contingent prompts were answered, data will be averaged across all event-contingent prompts during that period.
2. Data from all answered baseline and random [signal-contingent] EMA prompts will be considered.

Aim 1. For this aim, we will assess:

1. Compliance with the EMA prompts as indicated by the frequency of responses to prompts, specifically:
 - a. # of responses (complete:incomplete)/number of prompts
 - b. # times spirometer used/number of prompts
 - c. # times environment modified/number of event-contingent prompts
2. Compliance as described in 1a-1c by 4-hr each period.

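### Respiratory illness during the 14 days is not visibly recorded or modelled, so the Aim 3 VOC/PM2.5 associations with asthma outcomes may be biased in either direction, probably slightly

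*Combined protocol and SAP*

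**What the plan says.** The Specific Aims give the reason infection matters: "Viral infections are a prominent risk factor for asthma exacerbation".

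Baseline Measures, item 5 (Health and Demographics), holds the only infection item named in the text: "COVID-19 prevention practices, and COVID-19 exposure/infection status". It concerns COVID-19 only and is asked once. Other respiratory infections are not named at any time point.

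During follow-up, the repeated symptom item is "trouble breathing, wheezing, coughing, other symptoms [Yes:No]) assessed each time participants are asked to complete an EMA survey". The morning, random, alert-triggered and 30-minute surveys are otherwise described as covering disinfectant use, likely sources, mitigation and spirometer use. The seven-day check-in consists of "Open-ended questions to identify any trouble-shooting areas, determine if adjustments need to be made, and assess ease of use of the app/devices". No illness question is described in any of these. The item wording itself is deferred: "EMA survey items (See Appendix", and that Appendix is not in the text available for review.

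Data Analysis, Aim 3, lists three exposures: (1) baseline self-reported disinfectant/cleaner use and PM2.5 exposure; (2) weekly counts of VOC and PM2.5 readings beyond the optimal threshold; (3) average VOC and PM2.5 in the analysis windows. The outcomes are any asthma symptoms, inhaler use and FEV1% predicted. The adjustment set is: "We will control for level 1 variables (time of day, day of week) and level 2 variables (baseline asthma symptoms, demographic characteristics, and psychosocial characteristics". Neither illness nor calendar season is listed.

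**The concern.** A respiratory infection during the 14 days can produce cough, wheeze, inhaler use and a lower FEV1. If the same infection, in the participant or the household, also changes hours at home, cleaning or cooking, it moves VOC and PM2.5 as well. It is then a time-varying confounder of exposures (2) and (3). Person-level covariates and a person-level random effect cannot remove something that switches on and off within a person, and time of day and day of week do not track it.

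Between participants the question is different. Each person is observed for one fortnight in one place, so comparisons across people can carry season, circulating viruses and outdoor air. The Significance section makes the last of these concrete: "Common indoor sources of particulates include outdoor sources".

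At stake is how far an Aim 3 coefficient can be read as an effect of indoor air. Aim 3 is exploratory, but its results are intended to inform a powered study, and the Summary says findings could affect recommendations on using disinfectants and cleaners indoors.

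**Working it through.** The documents give no illness rate, effect size, alpha or power, so there is no plan figure to reproduce. The checks below use assumed values to show the possible size.

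**Inputs from the plan.** 50 participants, 14 days, four 4-hour windows per day: at most 50 × 14 × 4 = 2,800 person-windows.

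**Chance that the problem arises.** If a fraction p of participants falls ill, P(at least one of 50) = 1 − (1 − p)^50. For p = 2%, 5%, 10% and 20% this is 64%, 92%, 99.5% and over 99.9%, with 1, 2.5, 5 and 10 people expected.

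**Spurious odds ratio with no true exposure effect.** Assumed: symptoms in 70% of ill and 30% of other windows; high exposure in 40% of ill and 20% of other windows; illness lasts 5 of 14 days.

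- Share of ill windows: q = p × 5/14.
- P(ill | high) = 0.4q / [0.4q + 0.2(1 − q)].
- P(ill | not high) = 0.6q / [0.6q + 0.8(1 − q)].
- P(symptoms) in each group = 0.3 + 0.4 × P(ill | group).

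| Participants ill | q | P(symptoms), high | P(symptoms), not high | OR | log OR |
|---|---|---|---|---|---|
| 5% | 0.018 | 0.314 | 0.305 | 1.04 | 0.04 |
| 10% | 0.036 | 0.328 | 0.311 | 1.08 | 0.08 |
| 20% | 0.071 | 0.353 | 0.322 | 1.15 | 0.14 |

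With all 2,800 windows answered and treated as independent, the standard error of the log odds ratio (root of the summed reciprocal cell counts) is about 0.10. The first two rows therefore lie within one standard error, and the third is about 1.5.

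**Direction.** If ill windows have high exposure in 10% of cases instead of 40%, the same formulas give 0.98, 0.96 and 0.93. If illness leaves exposure at 20%, the odds ratio is 1.00.

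**Effect on false positives.** A simulation with zero true effect used 50 people × 56 windows, 1,500 runs per scenario, and a within-person linear model with person-clustered standard errors and a two-sided 5% test. Symptoms were fitted with a linear probability model as a stand-in for the planned multilevel logistic model. Assumed: illness lasts up to 7 days, lowers FEV1% predicted by 8 points (within-person SD 5), multiplies symptom odds by 4, and shifts exposure by the stated number of SDs. Entries are false-positive rates without → with an illness indicator.

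| Ill | Exposure shift | FEV1 | Symptoms |
|---|---|---|---|
| 5% | +0.5 | 5.5% → 4.3% | 5.3% → 5.5% |
| 5% | +1.0 | 8.6% → 4.9% | 6.3% → 4.5% |
| 10% | +0.5 | 9.0% → 5.3% | 6.0% → 4.9% |
| 10% | +1.0 | 21.7% → 5.5% | 9.3% → 4.3% |
| 20% | −0.5 | 20.7% → 4.5% | 10.7% → 4.5% |
| 20% | 0 | 4.9% → 4.9% | 5.6% → 6.2% |
| 20% | +0.5 | 22.2% → 4.9% | 11.3% → 5.0% |
| 20% | +1.0 | 58.0% → 5.6% | 26.3% → 4.1% |

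With 20% ill, the FEV1 bias is −0.17 points per SD of exposure for a +0.5 SD shift and +0.17 for −0.5 SD. Inflation is small at 5% ill, larger only when illness is common and moves exposure, and gone once illness is measured and modelled. The simulated indicator is error-free; a self-reported one would not be.

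**The case against.** Several stronger readings are tempting, and the documents do not support them.

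- **A false disinfectant–asthma association.** A reader might infer this from the protocol's premise. But the disinfectant exposure listed for Aim 3 is the baseline report, which an illness starting later cannot have caused. Real-time disinfectant reports are assigned to Aim 2a; the mechanism reaches them only if they are also modelled.
- **Bias towards harm.** The protocol ties extra cleaning and time at home to pandemic prevention, not to current illness, and says nothing about illness raising VOC or PM2.5. An ill person may clean or cook less. The sign is open.
- **A large bias.** Taking 5%, 10% or 15% of all windows as ill gives odds ratios of 1.11, 1.20 and 1.28. With 5-day illnesses that needs 14%, 28% or 42% of participants ill within their fortnight (share × 14/5). Setting q = 5/14 gives 1.45, but that describes one ill participant, not the pooled estimate.
- **Infection is certainly not collected after baseline.** The Appendix is unseen, and the summary of EMA items may be incomplete: inhaler use is an Aim 3 outcome, yet no described EMA item asks about it.
- **Season drives the within-person effect.** It is nearly constant over one person's 14 days. It matters between people, and only if enrolment spans seasons; no enrolment period is stated. Season terms (about 12 people per season among 50) also lengthen the level 2 list.

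It is also fair that a self-reported cold overlaps with cough and wheeze. A participant may label an exposure-triggered flare as a cold, so adjustment could remove a real effect. And Aim 3 is exploratory in a feasibility study.

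All of this narrows the point. What remains is that no described measure captures illness during follow-up and no level 1 covariate stands in for it.

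**Conclusion.** The concern holds in limited form. On the visible text, illness during the 14 days is neither recorded nor modelled, so the window-average and weekly-exceedance VOC/PM2.5 associations with symptoms, inhaler use and FEV1 are open to bias of either sign. The between-person part of those associations is also open to confounding by region, and by season if enrolment spans seasons.

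The size is probably small when few participants fall ill: about 1.04 to 1.15 on the odds-ratio scale for 5% to 20% ill. It becomes material in the simulation when about 20% are ill and exposure shifts by half an SD or more. These figures rest entirely on assumed illness rates, durations and effects. The point limits interpretation of Aim 3 and merits a cheap improvement; it does not touch feasibility (Aim 1) or the descriptive results (Aim 2).

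**What to change.** 1. Unless the EMA Appendix already has such an item, add one question to the existing morning survey on new cold, flu, fever or a positive COVID-19 test since the previous day (self / household / no). Report the Aim 3 VOC/PM2.5 models without it, with it as a day-level covariate, and with ill days excluded. State that self-reported colds overlap with the symptom outcome, so the adjusted results may be over-adjusted.
2. Split window-average VOC/PM2.5 into each participant's mean and the deviation from it, and report both effects. Read the between-person effect as open to confounding by season and region. The split does not remove illness confounding, which sits in the deviations; that is what item 1 addresses.
3. If enrolment spans seasons, add calendar season at level 2 from the existing time stamps.

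If data collection is complete, do 2 and 3 and state unmeasured illness as a limitation of Aim 3.

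Cost: about 14 extra taps per participant, some loss of precision when ill days are dropped, a few more model terms, and analysis-plan wording. Placing the item in the existing morning survey adds no prompt, which matters because community feedback led to fewer routine prompts per day.
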